## 6 RATIONALE AND BACKGROUND

### 6.1 BACKGROUND

Characterization of the long-term safety profile of Cerdelga in patients with GD has been identified as a mandatory (EU) pharmacovigilance activity, beyond routine pharmacovigilance. The objective is to collect these data from a less controlled environment than that of the clinical studies conducted so far. For this purpose, and to enable comparison of the Cerdelga safety profile to that of Cerezyme (which has been well established), a prospective ICGG safety sub-registry to collect long-term safety data in patients treated with Cerdelga or Cerezyme will be created. These long-term data should provide valuable information on the potential risks of Cerdelga, and may clarify whether certain AEs observed in the clinical studies are due to the underlying disease, to Cerdelga or to another cause. The sub-registry will also be used to describe patient characteristics and utilization patterns of Cerdelga by HCPs as a means to assess the effectiveness of the risk minimization measures (eg, local labelling and educational materials).

### 6.2 RATIONALE

This registry is set up as a sub-registry to complement the ICGG Gaucher Registry, a multi-center, international, longitudinal, observational program for patients with GD designed to track the natural history of the disease, and outcomes of patients on GD treatments. Similarly, using the same ICGG technology platform, the sub-registry is designed to follow patients on Cerdelga and Cerezyme and in particular assess the long-term safety profile of Cerdelga and descriptively compare it with Cerezyme by collecting real-world safety data as part of a post approval commitment.

Enzyme Replacement Therapies, such as Cerezyme, and SRTs, such as Cerdelga, are substitutive or corrective treatments that ameliorate disease manifestations, but do not eliminate the root cause of the disease. Therefore, it is assumed that long-term maintenance therapy with ERT or SRT is required for reaching or maintaining therapeutic goals. Though the studies supporting the registration of Cerdelga have continued to collect data for multiple years (up to 8 years for the Phase 2 study), an extended follow-up of patients treated in real-world clinical practice will support the longer-term safety of Cerdelga.

Clinical studies with Cerdelga have demonstrated a favorable benefit-risk profile, with robust efficacy results and a treatment that was generally well-tolerated across the clinical program. However, safety concerns were identified and include important potential risks and missing information.

#### Important potential risks:

- Drug-drug interactions:
  - Use with CYP2D6 and/or CYP3A inhibitors
  - Use with strong CYP3A inducers
  - Use with P-gp or CYP2D6 substrates

- Use of Cerdelga in patients who are CYP2D6 indeterminate metabolizers or non-genotyped patients
- Cardiac conduction disorders and arrhythmias

Missing information:

- Use in patients with a history of or current cardiac ischemia or heart failure, clinically significant arrhythmias or conduction findings
- Use during pregnancy and lactation
- Safety in long-term treatment use
- Use in patients who are CYP2D6 URM

Available published and unpublished data related to gaps in knowledge reflect the current information presented above and in the EU RMP.

Additional pharmacovigilance activities beyond routine to gather long-term safety data are needed to explore and further characterize this missing information. As European Authorities have identified the limited number of exposed patients, particularly in real-world experience and in the long-term, as a major concerned area of research given that Cerdelga is intended to be a chronic treatment, long-term data will provide a better understanding of the potential risks that were identified in clinical studies and may clarify whether these risks are due to Cerdelga treatment, the underlying GD, or another cause.

Finally, the sub-registry will allow assessment of clinical practice and prescribing patterns, and the adherence of prescribing HCPs to Cerdelga key label (prescribing information) requirements, and will provide data to assess the effectiveness of risk minimization measures. Key prescribing information requirements include testing the genotype and predicting the phenotype of the key metabolic pathway, CYP2D6, in each patient before starting treatment to guide dosing; excluding CYP2D6 indeterminate and URM from treatment; and prescribing Cerdelga only to patients with type 1 GD.

As the sub-registry is a voluntary program, the total number of patients who will participate and the total number of person-years of follow-up are not pre-defined, as not all patients have been identified, nor will all patients who could meet the study criteria may wish to participate. The sub-registry database has been designed to collect a variety of baseline and follow-up data obtained through routine clinical and laboratory assessments in the ICGG Gaucher Registry database. Each participating HCP is solely responsible for determining the appropriate clinical care for each patient. All data submissions are voluntary and there are no pre-determined follow-up periods. Participating sites will be encouraged to enter comprehensive baseline data at patient enrollment and to perform follow-up assessments at regular intervals, as described in the Recommended Schedule of Assessments of the ICGG Gaucher Registry. However, since this is a registry where data will be derived from routine clinical practice and not an interventional study, there will be no predefined diagnostic or monitoring procedures. Health Care Providers will decide what assessments to perform and when for each patient. Interviews, questionnaires and blood samples will be performed as in routine clinical practice.

In the sub-registry HCP's will be instructed to collect and report all AEs that occur during sub-registry participation, regardless of relationship to treatment.

The aim is to enroll as many patients on Cerdelga as possible.

Therefore, the only inclusion criteria for patients are:

- I 01. Male or female patient aged 18 years or older;
- I 02. The patient must be enrolled in the ICGG Gaucher Registry prior to safety sub-registry enrollment;
- I 03. The patient is willing and able to provide written informed consent for the safety sub-registry;
- I 04. The patient must have a confirmed diagnosis of GD, as defined in the protocol of the ICGG Gaucher Registry (documented acid  $\beta$ -glucosidase deficiency and/or mutations in the acid  $\beta$ -glucosidase gene);
- I 05. The patient must either initiate or continue treatment with Cerdelga or Cerezyme at the time of safety sub-registry enrollment.

The only exclusion criteria for patients are:

- E 01. The patient is concurrently enrolled in another clinical study; or participates in the compassionate use program with Cerdelga.
- E 02. The patient is treated with both Cerezyme and Cerdelga at the time of enrollment, or investigator consider treating patient with both therapies concurrently at any time during participation in the safety sub-registry.

Patients on Cerezyme will provide a control group to descriptively compare the safety profile of Cerdelga to that of Cerezyme.

Both Cerdelga and Cerezyme are currently first line treatment for GD1 and thus expectedly both will be prescribed as such to GD1 patients. Miglustat is approved as second line SRT, for patients for whom ERT is unsuitable. Comparison of Cerdelga with miglustat would create a bias when trying to use miglustat as the comparator, since Cerdelga does not have the limitation of only to be prescribed to patients for whom ERT is not a therapeutic option. Thus, the underlying patient population will be different for those eligible to receive Cerdelga versus miglustat, and any subsequent analyses will be biased by design. In the real clinical practice the number of patients on miglustat would be insufficient to provide a viable comparison group due to the reduced current use of miglustat, which is expected to continue decreasing. For these reasons, Cerezyme and not miglustat has been chosen as comparator group.

## 7 RESEARCH QUESTION AND OBJECTIVES

### 7.1 PRIMARY OBJECTIVE

The primary objectives:

1. To evaluate the long-term safety of Cerdelga in real-world clinical practice.
2. To describe the utilization of Cerdelga.

The long-term safety of Cerdelga will be evaluated by the incidence rate of any AE during sub-registry participation, whether considered related or unrelated to Cerdelga by the treating HCP. The risk of an AE compared to Cerezyme will be evaluated in terms of the risk ratio (ratio of incidence rates).

Evaluation of utilization patterns of Cerdelga includes:

- To assess compliance/adherence of HCPs to the labelling with regard to CYP2D6 genotyping prior to initiation of Cerdelga
- To assess compliance/adherence of HCPs to the Cerdelga label with regard to patients' CYP2D6 predicted phenotype
- To assess compliance/adherence of HCPs to the Cerdelga label with regard to use in GD type 1.

In order to avoid the introduction of an element of positive or negative bias into the safety reporting from the ICGG Gaucher Registry physicians by providing a specific list of safety issues to be collected (and subsequently recorded in the CRFs) in protocol, there will be no suggested areas of safety data collection. Rather all safety data will be collected and subsequently assessed in relation to the important potential risks in the RMP. All AEs for Cerdelga and Cerezyme, regardless of their relation to treatment will be collected. However, when the safety analysis will be performed, specific exploratory analyses of the potential risks listed in RMP and any new safety concern that could arise from the sub-registry, will be included and reported in the PSUR in the EU regional annex.

## 8 RESEARCH METHODS

### 8.1 STUDY DESIGN

This is a safety sub-registry of the ICGG Gaucher Registry (DIREGC07009).

This is a non-interventional, multicenter, prospective PASS of Cerdelga, a treatment approved in many countries for adult patients with GD1 who have a CYP2D6 PM, IM, or EM phenotype. Participating HCPs will enroll eligible patients after the decision to treat with Cerdelga or Cerezyme. The study will enroll patients who will be receiving Cerdelga or Cerezyme for the first time or as part of ongoing treatment of their GD.

Patients will receive treatment as determined by the patient's HCP and guided by the provisions of the prevailing locally approved product labelling and educational materials, and the ICGG Gaucher Registry recommendations for monitoring. All treatment decisions and medical assessments are at the discretion of the HCPs and are not mandated by study design or protocol.

No experimental intervention is involved. Participating patients will undergo clinical assessments and receive the standard of-care treatment for GD, as determined by their treating HCPs, who may want to use the Gaucher registry Recommended Schedule of Assessments as a guideline. The observational nature of this study design will allow for an estimate of 'real world' safety experience of Cerdelga among patients who receive Cerdelga in a commercial versus clinical study setting.

Patients will complete and sign a patient written Informed Consent Form specific to this safety sub-registry before participating.

Selected data from the sub-registry CRFs will be monitored periodically against source documents at the treating HCP's site by a representative of Sanofi Genzyme (or its designee) to ensure data completeness and accuracy. Refer to [Section 8.7.2](#) for further details.

Study baseline will be defined as the time of entry into the sub-registry.

### 8.2 SETTING

This is a non-interventional, international, multicenter, prospective PASS of Cerdelga, a treatment approved in many countries for adult patients with GD1. The aim of the study is to collect long-term safety data from the ICGG Gaucher Registry for patients treated with Cerdelga and Cerezyme. HCPs will enroll eligible patients after the decision to treat with Cerdelga or Cerezyme. As Cerdelga is not approved for pediatric patients, only adult patients are included in this study. There is no set duration for this study. The number of patients for both of the groups who continue their observation in the sub-registry will be evaluated annually after the end of the recruitment period to determine the need to replace patients who dropped out of the study for any reason. The need to continue with this requirement will be reassessed two years after the last Cerdelga patient has been enrolled in the study in the interim report. Data collection will be concluded four years after the last Cerdelga patient has been enrolled in the study. The sub-registry study patients will be recruited from sites in countries where Cerdelga is already on

the market or will become available on the market during the sub-registry enrollment period. Both ICGG Gaucher Registry sites and new sites, which could potentially become ICGG Gaucher Registry sites, will be considered for the study. Health Care Providers at these sites who manage patients with GD1 will be invited to participate in the sub-registry.

At least 100 patients on Cerdelga will be representative of the entire population of GD1 adult patients treated with Cerdelga in countries where Cerdelga is on the market or is expected to become available on the market within the enrollment period of the study (the sample size justification is further discussed in [Section 8.6.1](#)). The ratio of Cerdelga versus Cerezyme patients recruited for the study is planned to be approximately 2:1.

There is no predefined number of sites which are planned to be opened for this sub-registry, nor is there a predefined number of patients to be enrolled per site. The final number of sites will ensure achievement of enrollment goals for the set duration of the recruitment. The patient recruitment will be EU focused to represent GD1 patients treated with Cerdelga in the EU. Depending on study enrollment during the recruitment period, other countries and regions where Cerdelga has a marketing authorization (eg, USA, Israel) will also be considered.

List of countries where data will be collected may depend on the actual dates when Cerdelga will become available on the market in particular country. Potential countries for safety sub-registry could include Germany, Denmark, France, United Kingdom, Italy, the Netherlands, Belgium, Portugal, Sweden, Spain, Czech Republic, and Romania. There is no limit of patients or sites per country. However, every effort will be made to ensure equal representation of patients per country to represent the real-world safety profile of Cerdelga with the majority of patients recruited in the EU. Data collection in the sub-registry is planned to start approximately 6 months after PRAC protocol approval has been obtained.

Inclusion criteria (see [Section 8.2.2.1](#)) for the study are very wide to enable HCP's to enroll as many adult patients treated or to be treated with Cerdelga or Cerezyme as possible in order to collect data in as many patients as possible. The exclusion criteria are limited only to patients currently enrolled in another clinical study (especially any receiving Cerdelga as part of that study) and patients treated with Cerezyme and Cerdelga in combination at the time of enrollment.

Patients who have been exposed to Cerdelga in clinical studies prior to their enrollment in the sub-registry can be enrolled in any group of the sub-registry and will be considered as experienced to Cerdelga. Their previous exposure to Cerdelga in clinical studies will be considered and described, notwithstanding the group of treatment these patients belong to during the safety sub-registry.

The data for enrolled patients who switch treatment from Cerdelga to Cerezyme or vice-versa during the follow-up will be evaluated to and from the point of switch in the therapy (if applicable).

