#### **8.4 STATISTICAL ANALYSIS**

Adverse events, SAEs, and events of interests will be summarized by treatment group, and by the three categories of treatment status and treatment group using percentage and frequency. For abnormal laboratory results assessed as AEs (clinically significant abnormal laboratory results), reported values of laboratory results in the course of AE follow-up will be summarized descriptively, including mean, standard deviation (SD), median, minimum and maximum. Categorical or qualitative variables will be summarized using percentages and frequency distributions. Timing of CYP2D6 genotyping and prevalence of CYP2D6 predicted phenotypes and GD subtype among Cerdelga-treated patients will be summarized using percentages and frequency.

In addition, the 95% confidence interval of incidence rates will be provided by treatment group. The risk of any AE in the Cerdelga group compared to Cerezyme will be evaluated in terms of the risk ratio with associated 95% confidence interval.

Data will be analyzed as available, missing data will not be imputed. For all AEs summary statistics, frequencies, cumulative incidence, and incidence rates per person-time will be calculated as appropriate. All summaries will be descriptive; no formal hypothesis testing will be performed.

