### **8.6.2 Sample size**

In countries where Cerdelga will be available on the market at least 100 Cerdelga patients will be recruited in the study and approximately 50 Cerezyme patients will be included in the control group of safety sub-registry to descriptively compare the safety profile of Cerdelga to that of Cerezyme.

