## **8.7 DATA MANAGEMENT**

### **8.7.1 Data collection schedule**

Data will be collected from enrolled patients by participating HCPs at the time of all patient office visits occurring as per local practice visit schedule or following the recommended schedule of assessments of the ICGG Gaucher Registry. Adverse events should be collected from patients at least every 6 months. If the period of time between the last ELISAFE sub-registry assessment and the next planned ICGG Gaucher Registry assessment is expected to be more than 6 months, a phone call to inquire about new/ongoing AEs is recommended.

If a patient temporarily stops (for any reason) treatment with Cerdelga or Cerezyme and the treating physician considers that the treatment can be potentially restarted, the patient can stay in the sub-registry as long as the sub-registry is open, the patient is willing to participate and is available for follow-up assessments. Collection of all AEs will be continued for the duration of 30 days after stopping Cerdelga or Cerezyme, and after that period only new SAEs will be collected and follow-up of ongoing AEs will be performed. Collection of all AEs in ELISAFE will be resumed when the patient restarts treatment with Cerdelga or Cerezyme.

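### The Cerdelga/Cerezyme AE rate ratio is not stratified by country or site, so it may partly reflect where each product's patients were recruited

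*Combined protocol and SAP*

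**What the plan says.** **Recruitment.** Section 8.2 gives the product ratio for the study as a whole: "The ratio of Cerdelga versus Cerezyme patients recruited for the study is planned to be approximately 2:1". Section 8.6.2 gives the numbers: "at least 100 Cerdelga patients will be recruited in the study and approximately 50 Cerezyme patients will be included in the control group". For sites, 8.2 adds "nor is there a predefined number of patients to be enrolled per site", and for countries, "There is no limit of patients or sites per country". It does have one country-level aim: "every effort will be made to ensure equal representation of patients per country to represent the real-world safety profile of Cerdelga". That aim concerns the number of patients per country, not the split between products within it. The list of countries "may depend on the actual dates when Cerdelga will become available on the market in particular country". Patients enrol after their physician has chosen the product (8.1, 8.2).

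**AE ascertainment.** Section 8.7.1 has data collected "at the time of all patient office visits occurring as per local practice visit schedule", or by the parent registry's recommended schedule. AEs should be obtained at least every 6 months, with a recommended phone call when the gap would be longer. Section 8.9.2 provides for checking CRFs against source documents and for quality control at all active sites.

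**Analysis.** Section 8.4 states "The risk of any AE in the Cerdelga group compared to Cerezyme will be evaluated in terms of the risk ratio", with a 95% confidence interval. Section 7.1 defines this as a ratio of incidence rates. The grouping factors named in 8.3 are treatment status, prior duration of Gaucher treatment, and characteristics such as age, sex and genotype. Neither country nor site is named. The only stratification of AEs described in 8.4, 8.8 and 8.10 is by the three treatment-status categories.

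**The concern.** Two things can vary from place to place: the share of patients on each product, and how completely AEs are elicited and recorded. If both vary together, the crude ratio mixes a product difference with a difference in reporting between places. This is confounding by place. Grouping by patient characteristics does not deal with it directly, because reporting practice belongs to the site and not to the patient.

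The rate ratio is the only between-product effect measure that the plan names, and section 6.1 says the Cerezyme patients are there to allow the comparison. The confidence interval would not reveal a shift of this kind, and the limitations in 8.10 do not mention it. What is at stake is how the ratio is read, not type I error or power, since the study is descriptive and tests no hypothesis.

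**Working it through.** **The plan's own figures.** 100/50 = 2, so the numbers in 8.6.2 agree with the 2:1 in 8.2. The precision statement in 8.6.1 also reproduces: 1 − 0.95^100 = 0.994, which is above 95%. It concerns Cerdelga alone and does not bear on the comparison. The expected ratio of about 1.2 is taken from 8.6.1 as stated.

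**Inputs the documents do not give.** These are assumed throughout:
- p1 and p0: the shares of Cerdelga and Cerezyme person-time that come from higher-reporting countries
- R: AEs recorded per person-year in higher-reporting countries, relative to the others
- uniform reporting within each group of countries

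**Crude ratio with no product effect.**

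Crude ratio = (p1·R + 1 − p1) / (p0·R + 1 − p0)

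| p1 / p0 | R = 1.5 | R = 2 | R = 3 |
|---|---|---|---|
| 60% / 50% | 1.30/1.25 = 1.04 | 1.60/1.50 = 1.07 | 2.20/2.00 = 1.10 |
| 70% / 40% | 1.35/1.20 = 1.13 | 1.70/1.40 = 1.21 | 2.40/1.80 = 1.33 |
| 50% / 60% | 1.25/1.30 = 0.96 | 1.50/1.60 = 0.94 | 2.00/2.20 = 0.91 |
| 40% / 70% | 1.20/1.35 = 0.89 | 1.40/1.70 = 0.82 | 1.80/2.40 = 0.75 |

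The shift can therefore run either way: 1.04 to 1.33 in the first two rows, 0.75 to 0.96 in the last two.

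**Do equal patient totals protect the ratio?** Take two groups of sites, A and B, with 75 patients each, 100:50 overall, equal follow-up and no product effect. A reports k times as many AEs as B.

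- Product mix 50:25 in both groups: the crude ratio is 1.00 for every k.
- Mix 60:15 in A and 40:35 in B, k = 2: Cerdelga (60·2 + 40)/100 = 1.60; Cerezyme (15·2 + 35)/50 = 1.30; ratio 1.60/1.30 = 1.23. For k = 1.25, 1.5 and 3 the ratio is 1.07, 1.13 and 1.38.
- The same mix with a true ratio of 1.2 and k = 2: 1.2 × 1.23 = 1.48.

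Equal totals per place are thus not enough; the product mix within each place is what matters.

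**Stratified ratio.** For the 60:15 and 40:35 mix at k = 2 with no product effect, the Mantel-Haenszel numerator is 120·15/75 + 40·35/75 = 42.67. The denominator is 30·60/75 + 35·40/75 = 42.67. The ratio is 1.00. This is exact only because reporting was assumed uniform within each group.

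**Sparseness.** Section 8.2 lists 12 possible countries. Spread evenly, 50 Cerezyme patients give 50/12, or about 4 per country.

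**The case against.** The strongest reply is that the plan already limits reporting differences. It asks for AEs at least every 6 months, uses a dedicated set of CRFs, checks them against source and covers every active site with quality control. These measures help and deserve weight. They do not remove the problem: the phone call is only recommended, the assessments themselves are left to local practice (6.2), and a source check cannot recover an AE that was never elicited. The equal-representation aim in 8.2 is also a real country-level aim, but it is a best effort on totals and is silent on product mix.

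A second reply is that the primary endpoint is the Cerdelga incidence rate and the comparison is only descriptive. That stands as a limit on importance. A descriptive ratio can still be biased, though, and this one will be reported with an interval.

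Third, stratification has limits of its own. Strata will be sparse, and stratifying by country leaves differences between sites within a country. This is a good reason to keep the crude ratio and put the stratified one beside it, not in its place. Fourth, Q2 2018 plus 32 months (section 5) puts the end of recruitment close to this December 2020 version, so new recruitment targets would come too late. The analysis can still change.

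A reader might infer two stronger points that the documents do not support:
- That AE rates are known to depend strongly on site or country. No such rates are given.
- That countries awaiting Cerdelga launch will supply only Cerezyme patients until then. No section says that sites enrol before launch, and sections 3 and 8.6.2 tie recruitment to countries where Cerdelga will be available.

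**Conclusion.** The point holds as a gap in the analysis. Product choice is not controlled within country or site, AE ascertainment is partly local, and the ratio in 7.1 and 8.4 is not stratified by either. It may therefore partly reflect the recruitment map.

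The size cannot be derived from the documents. Under the assumed shares and reporting ratios, the shift runs from negligible (1.04) to larger than the whole expected excess (1.33 against about 1.2), and equally to below 1 if the shares are reversed. It would be wrong to conclude that the ratio will be inflated, or that a result near 1.2 would be an artefact. The product-specific rates remain what the plan says they are; only the contrast between them is affected. The change is worth making because it touches only the analysis.

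**What to change.** **In 8.4:** report, beside the crude ratio, a Mantel-Haenszel person-time rate ratio stratified by country. Pool small countries into regions fixed before the analysis, and use a confidence interval that allows for repeated AEs within a patient.

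**Tables:** show patients, person-years and AEs by product, by country and by site. List strata with one product only, and state that they contribute to the product-specific rates but not to the stratified ratio.

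**In 8.10:** name remaining differences between sites within a country as a limitation.

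**Cost:** plan wording, one additional estimate and its tables. The stratified ratio will have a wider interval, and single-product strata drop out of it. Recruitment, visits and data collection do not change.
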